## **Mastectomy Flap Temperature and Clinical Implications**

Wake Forest Baptist Comprehensive Cancer Center

WFBCCC # 74222

### **6.3 Data Analyses**

This study will provide quantitative data on consent (proportion of all eligible patients approached who consent to having flap temperatures measured intra-operatively), and on ability to successfully measure all 12 flap temperatures (per breast) on patients who have consented.

We will calculate 95% confidence intervals for each of the above feasibility measures to determine the range of estimates that are consistent with our data. We will use one-sample tests of binomial proportions to compare the consent and successful measurement proportions to the hypothesized values of 60% and 90%, respectively.

We will examine intra-individual variability in flap temperature measurements by quadrant and by breast; we expect these sources of potential variability to be weak, controlling for time point of measurement (pre vs post mastectomy vs pre-implantation). We will derive average flap temperatures for each of the three time points separately. We will compare average flap temperatures at each of the three time points during surgery to average core body temperature at that time, using paired t-tests for the differences in means in a single sample. Our hypothesis is that, across all three time points, average flap temperatures will be lower than average core body temperatures, and that as time goes on during surgery, from pre- to post-mastectomy to pre-implantation, we expect average flap temperatures will be lower than average core body temperatures by a larger degree, as we expect flap temperatures to cool more quickly during surgery than overall body temperature.

In our exploratory analyses, we will document the occurrence and major and minor wound/surgical complications over the 90-day period following surgery and will examine whether there is a relation between the number of such complications per patient and 1. the patient's magnitude of difference between average flap temperatures and core body temperatures, and 2. the patient's absolute average flap temperatures .

.

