## 6.0 STATISTICAL CONSIDERATIONS

### 6.1 General Design Issues

This is a non-randomized prospective observational pilot study.

1. **Primary Hypotheses:** We hypothesize that at least 60% of eligible patients will consent to having flap temperatures measured intraoperatively, and that we will successfully measure all relevant temperatures (12 per breast) on at least 90% of those consenting. Both of these measures must be achieved to deem a future study feasible.
2. **Secondary hypotheses:** We hypothesize that we will observe a significant difference between average mean flap temperature and average core body temperature.
3. **Exploratory analyses:** We will describe post-surgical complications over the 90-day post-surgery period as frequencies.

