### 6.2 Sample Size

Our target sample size of 30 eligible patients, expected to be accrued over a period of 3-6 months, is based on our primary goals of examining feasibility measures to inform the design of a larger intervention trial. An n of 30 will provide reasonably tight estimates of our parameters of interest. We will be able to estimate these proportions within 19.4% (for the lower CI bound; the window is smaller for the upper bound) using a two-sided 95% confidence interval. If the consent proportion is below 40.6% (fewer than 12 women consenting out of the 30 eligible), or the success in measuring all flap and peri-incisional temperatures occurs in fewer than 65% of the expected n=18 (i.e., fewer than n=11 women out of the starting pool of 30), we will conclude that a larger study of flap temperatures may not be feasible.

Power calculations for a subsequent larger study will be based on clinically and statistically meaningful differences between average flap temperatures and core body temperatures and will be informed by measures obtained in this pilot.

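### The 6.3 binomial tests have no stated role, the 90% test cannot confirm its target at 18 consenters, and the 6.2 no-go counts are each one too low for their own percentages

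*Combined protocol and SAP*

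**What the plan says.** Three places in the combined protocol and SAP bear on the primary feasibility verdict.

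- **Section 6.1 (General Design Issues)** sets the targets: "at least 60% of eligible patients will consent to having flap temperatures measured intraoperatively", and complete measurement "on at least 90% of those consenting". It adds: "Both of these measures must be achieved to deem a future study feasible". This is the go criterion.
- **Section 6.2 (Sample Size)** starts from "Our target sample size of 30 eligible patients" and sets a floor below which a larger study is judged possibly infeasible. For consent, the floor is 40.6%, glossed as fewer than 12 of the 30. For measurement, it is "fewer than 65% of the expected n=18 (i.e., fewer than n=11 women out of the starting pool of 30". On precision it says "We will be able to estimate these proportions within 19.4" percentage points on the lower side, "using a two-sided 95% confidence interval".
- **Section 6.3 (Data Analyses)** plans 95% confidence intervals for both proportions and then adds "one-sample tests of binomial proportions to compare the consent and successful measurement proportions to the hypothesized values of 60% and 90" percent. It gives no direction, no significance level and no statement of what a significant or non-significant result would mean for the verdict.

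**The concern.** Feasibility is the primary question and decides whether a larger study follows. A reader of the results will see point estimates set against 6.1, counts set against 6.2, and p-values from 6.3, with nothing to say how the p-values relate to the other two.

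Two misreadings are then easy. A non-significant test against 90% may be reported as the target being met. A result may also be reported as significantly below target and, in the same paragraph, as not infeasible. If the role of the tests is settled only once the data are in, the more convenient reading can be chosen.

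Separately, if the counts in 6.2 do not match the percentages beside them, some results are no-go by one half of the sentence and not by the other.

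**Working it through.** **Inputs.** 30 eligible patients, 18 expected consenters (0.60 × 30), floors of 40.6% and 65% with counts 12 and 11 (all 6.2); targets of 60% and 90% (6.1, and null values in 6.3). Assumption: the tests use the conventional 0.05 level. The only hint in the plan is the 95% level of the intervals, so one- and two-sided versions are both shown.

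**1. The plan's own figures.** The exact (Clopper-Pearson) 95% interval for 18/30 is 40.60% to 77.34%. The lower distance is 60 − 40.60 = 19.40 points, which reproduces both 19.4 and 40.6%. The upper distance is 17.34 points. For 16/18 the exact lower bound is 65.3%, which matches the 65% floor. The floors are therefore exact lower confidence bounds around roughly the target values.

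**2. Counts against percentages in 6.2.**

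- Consent: 0.406 × 30 = 12.18, so being below 40.6% means 12 or fewer. The count says fewer than 12, that is 11 or fewer. 12/30 = 40.0% is below the percentage but escapes the count.
- Measurement: 0.65 × 18 = 11.7, so being below 65% means 11 or fewer. The count says fewer than 11, that is 10 or fewer. 11/18 = 61.1% is below the percentage but escapes the count.

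**3. The count of 11 when the number consenting is not 18.** With 25 consenters, 11/25 = 44% clears the count. With 12 consenters (who clear the written consent count), 10/12 = 83% fails it. With 13 consenters (43.3% of 30, above either form of the consent floor), 10/13 = 77% fails it.

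**4. Can the 90% test succeed upward?** The best possible result with n consenters has upper-tail p = 0.9^n.

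- n = 18: 0.9^18 = 0.150 one-sided; two-sided 0.248 (minimum-likelihood) or 0.300 (doubled tail). Exact 95% lower bound 81.5%.
- Smallest n for one-sided p ≤ 0.05: 0.9^28 = 0.0523 and 0.9^29 = 0.0471, so 29 consenters out of 30 eligible, with no failure.
- Two-sided, even 30/30 gives p = 0.068.

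**5. Downward results at n = 18 against 90%.** Here the minimum-likelihood two-sided p equals the one-sided p.

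| Result | Exact p | Doubled-tail p | Exact 95% CI | 6.2 count | 6.2 percentage |
|---|---|---|---|---|---|
| 11/18 (61.1%) | 0.0012 | 0.0023 | 35.7% to 82.7% | clears | no-go |
| 12/18 (66.7%) | 0.0064 | 0.0128 | 41.0% to 86.7% | clears | clears |
| 13/18 (72.2%) | 0.028 | 0.056 | 46.5% to 90.3% | clears | clears |
| 14/18 (77.8%) | 0.098 | 0.196 | 52.4% to 93.6% | clears | clears |

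All four miss the 6.1 target, since 0.90 × 18 = 16.2 requires at least 17. The 12/18 result is below 90% under every exact version and clears the floor by count and by percentage. The 13/18 result rejects 90% only under some versions: the doubled-tail p exceeds 0.05 and the exact interval just includes 90%. The 14/18 result is non-significant although the estimate is 12 points short of the target.

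**6. Consent.** 12/30 against 60% gives exact two-sided p = 0.038 (doubled tail 0.042; CI 22.7% to 59.4%). The count lets it through; the 40.6% wording does not.

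**The case against.** A reader might infer that 6.2 and 6.3 return opposite verdicts on the same data. The documents do not support that. Section 6.2 is a one-directional floor and never calls a result above it feasible; section 6.3 attaches no verdict to its tests. A result can be significantly below 90% and still above the floor without contradiction, as long as a middle zone is understood. For 12/30 and 11/18, the tension with the test disappears once the percentages in 6.2 are followed, and 13/18 depends on the test version. Only 12/18 stands apart under every exact version and both wordings.

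A reader might also infer that no result at 18 consenters could satisfy the 90% hypothesis. That goes too far. Section 6.1 asks that the target be achieved, and 17/18 (94.4%) or 18/18 achieves it on the point estimate. What cannot happen is a significant upward rejection, which 6.1 does not require.

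It can further be said that this is a small pilot with confidence intervals already planned, that 18 is only an expected number, and that the 11 was meant as an absolute yield from the pool of 30. The first two points are fair and limit the severity. The third does not rescue the count, because the text presents it as the equivalent of 65% of 18, which is 11.7.

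What remains is that the middle zone is never stated, the tests have no defined role, and the counts do not match their percentages.

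**Conclusion.** The point holds in a limited form and should be fixed; it does not undermine the design. First, the tests in 6.3 lack direction, level and role, and at the expected 18 consenters the one against 90% can only reject downward or be non-significant (best case one-sided p = 0.150). Non-significance is uninformative about meeting the target, as 14/18 shows. Second, no sentence says how a result such as 12/18, significantly short of 90% but above the floor, is to be classified. Third, each count in 6.2 is one below what its percentage implies, and the fixed count of 11 departs from 65% whenever the number consenting differs from 18.

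The test results rest on an assumed 0.05 level and on 18 consenters. The count errors rest on neither assumption: they follow from the numbers in 6.2 alone.

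**What to change.** - **6.2, counts:** for consent, write fewer than 13 of 30 (12 or fewer). For measurement, write fewer than 65% of the women who actually consented (11 or fewer if 18 consent).
- **6.1 and 6.2, verdicts:** state that go means both 6.1 targets are reached on the point estimates, no-go means either 6.2 floor is breached, and anything between is reported as intermediate.
- **6.3, inference:** name exact (Clopper-Pearson) 95% intervals as the basis for inference. Drop the binomial tests, or label them exact and descriptive with no part in the verdict.

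**Cost.** Wording only, with no added patients or data. Slightly more results will be called infeasible or intermediate. If true consent is 60%, the chance of breaching the consent floor rises from 0.8% (11 or fewer of 30) to 2.1% (12 or fewer). If true measurement success is 90% with 18 consenters, the chance of breaching that floor rises from 0.02% (10 or fewer) to 0.12% (11 or fewer).

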To date there has been no study that has examined the feasibility of objectively quantifying the temperature of mastectomy flaps, or that has studied the relation between flap temperatures and core body temperature. This pilot study seeks to establish foundational evidence related to the feasibility of measuring temperatures of mastectomy flaps and to quantify the relation between flap and core temperatures. Specifically, we hypothesize that 1. we will be able to obtain consent from at least 60% of women undergoing therapeutic or prophylactic mastectomy (unilateral or bilateral, with reconstruction) to obtain flap temperatures intraoperatively, both pre- and post-mastectomy (note that core body temperature is measured continually as a usual aspect of intraoperative procedure, and thus does not require specific additional consent); 2. we will be able to successfully measure flap temperatures in 4 quadrants of relevant breast tissue (one or both breasts, depending on unilateral vs bilateral surgery) at each time point on at least 90% of those who do consent; and 3. average mastectomy flap temperatures will be significantly lower than core body temperature in this pilot sample.

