### **2.2 Secondary Objective(s)**

- 2.2.1 To measure mastectomy flap temperatures in 4 quadrants pre-mastectomy, following mastectomy, and pre-implant, and compare average flap temperature to average core body temperature.

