All patients of the age of 18 or above that are scheduled for mastectomy and implant-based breast reconstruction and who meet our remaining eligibility requirements will be screened for our study and enrolled if they consent. If the patient meets eligibility requirements a study team member will reach out to them via a telephone call prior to their surgery date. If the patient expresses an interest in taking part in the study a study team member will meet with them in the pre-op holding room the day of surgery to obtain written informed consent. To address our feasibility objectives, we plan to record the medical record numbers of patients who decline participation in the study. Clinical data and patient information will be entered into an encrypted, password protected database by approved study personnel. The type of information that will be collected and entered into the database will include (but not be limited to) that shown below in Table 1. The database will be updated with pertinent information for each subject after each surgery and postoperative visit on an intermittent basis. The intraoperative data points will be collected through the use of a myocardial temperature probe (See Section 6.1.1 and Figure 1) introduced into the 4 quadrants. This is a disposable temperature sensor. One sensor will be utilized for each patient. The flap temperatures will be collected by the research staff. There will be a hard stop on the probe at 4mm of depth in order to assess the temperature of the subdermal plexus upon which the mastectomy flap will be perfused. Core temperature will be assessed simultaneously using standard-of-care anesthesiologist-mediated methods involving a temperature probe placed in the nasopharynx. For this study specifically, core temperatures will be recorded at the same time intervals as the localized mastectomy flap temperatures are obtained.

**OF NOTE:** Due to risk of puncturing the implant with the myocardial temperature sensor post implant placement, flap temperatures at this time point will not be collected. If a pre-implant temperature is missed, post-implant flap temperatures are not allowed.

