**Table 1: Data Points to be Collected**

Preoperative	

- MRN

- Age

- BMI

- Smoking status

- Diabetes Mellitus

- Neoadjuvant radiation

- Neoadjuvant Chemotherapy

- Tumor type and stage

Intraoperative	

- Mastectomy weight

- Size of tissue expander or implant placed

- Number of drains placed

- Temperature collection:

- Pre-mastectomy - core temp and flap temp in 4 quadrants

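### Section 6.3 hypothesises that the flap–core temperature gap widens during surgery, but no planned analysis estimates or tests the change in the gap

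*Combined protocol and SAP*

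**What the plan says.** The hypothesis in section 6.3 has two parts. The first is that flap temperature lies below core temperature at all three time points. The second is that "from pre- to post-mastectomy to pre-implantation, we expect average flap temperatures will be lower than average core body temperatures by a larger degree", because flaps are expected to cool faster than the body.

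The method in the same section is to compare average flap temperatures "at each of the three time points during surgery to average core body temperature at that time, using paired t-tests". Averages are derived for each time point separately. Time point enters the analysis text in one other place, as an adjustment when variability by quadrant and breast is examined. The only confidence intervals planned are for the two feasibility proportions.

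Other sections state only the flap–core difference:

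- Section 1.0: "average mastectomy flap temperatures will be significantly lower than core body temperature in this pilot sample".
- Objective 2.2.1: "compare average flap temperature to average core body temperature".
- Section 6.1, secondary hypothesis: "we will observe a significant difference between average mean flap temperature and average core body temperature".

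The data for a comparison over time will exist. Section 5.1 says that "core temperatures will be recorded at the same time intervals as the localized mastectomy flap temperatures are obtained", and Table 1 lists core and four-quadrant flap readings at each time point, beginning with "Pre-mastectomy - core temp and flap temp in 4 quadrants".

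**The concern.** The second half of the hypothesis concerns a change in the gap between time points. A t-test at one time point says nothing about that change, and three such tests do not add up to one that does. A reader will be given three mean gaps and will compare them by eye. If the true gap is constant, the pre-implant mean still exceeds the pre-mastectomy mean half the time by chance, and nothing planned shows whether an apparent widening is more than noise.

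Nor can the exact interval for the change be rebuilt from three mean gaps and their SDs. It depends on the within-patient correlation between time points, which is not planned for reporting. At stake is one secondary claim, that flaps lose heat faster than the body as surgery proceeds. The primary feasibility aims are not involved.

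**Working it through.** **Inputs.** The plan gives no SD, gap, correlation or power for the temperature comparisons, so it has no figure of its own to reproduce here. The number of patients comes from section 6.2 ("fewer than 65% of the expected n=18"), which is 60% of 30. All SDs and gaps below are assumptions, shown over a range. Gap means core minus mean flap, and SD is the SD of the within-patient change in gap.

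**1. Precision of the missing contrast.** Half-width of the 95% CI = t(0.975, 17) × SD / √18, with t = 2.110 and √18 = 4.243. For SD = 0.8: 2.110 × 0.8 / 4.243 = 0.398 °C.

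**2. Chance of an apparent widening when the gap is constant.** P(observed change ≥ 0.2) = 1 − Φ(0.2 / (SD/√18)). For SD = 0.8 the standard error is 0.189, giving 1 − Φ(1.06) = 0.144.

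**3. Power of a paired t-test on the change**, two-sided 0.05, noncentral t with noncentrality change × √18 / SD. For a 0.5 °C overall widening and SD = 0.8 this is 0.5 × 4.243 / 0.8 = 2.652, and power is 0.705.

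| SD of change (°C) | 95% CI half-width (°C) | P(apparent widening ≥ 0.2 °C), constant gap | Power, 0.5 °C overall | Power, one 0.25 °C step |
|---|---|---|---|---|
| 0.6 | 0.298 | 0.079 | 0.915 | 0.385 |
| 0.8 | 0.398 | 0.144 | 0.705 | 0.240 |
| 1.0 | 0.497 | 0.198 | 0.516 | 0.170 |

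**4. Dependence on correlation.** If the gap has SD 0.8 °C at each time point, the SD of change is 0.8 × √(2(1 − ρ)). For ρ = 0.2, 0.5 and 0.8 the half-width is 0.503, 0.398 and 0.252 °C. The same three reported SDs are thus compatible with intervals differing twofold in width.

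**5. What the planned tests show.** Simulation with 100,000 trials per case, 18 patients, between-patient SD 0.6 °C, and within-patient SD equal to the SD of change divided by √2. Results are for SD of change 0.6 / 0.8 / 1.0 °C.

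| Quantity | Constant gap, 1.25 °C | Widening gap, 1.0, 1.25, 1.5 °C |
|---|---|---|
| All three t-tests significant, flap lower | 1.000 / 1.000 / 0.999 | 1.000 / 0.998 / 0.990 |
| Pre-implant mean gap above pre-mastectomy | 0.500 / 0.500 / 0.499 | 1.000 / 0.996 / 0.983 |
| 95% CI for the change wholly above zero | 0.025 / 0.026 / 0.024 | 0.915 / 0.709 / 0.517 |

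Under the constant gap, the three means rise in order in 0.168 / 0.166 / 0.166 of trials, which is the 1 in 6 expected from symmetry. The significance pattern of the planned tests is nearly the same in both scenarios. The contrast is what separates them.

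**The case against.** The strongest reply is that little depends on this. The widening statement occurs once, in 6.3. It is absent from the introduction's numbered hypotheses, objective 2.2.1 and the secondary hypothesis in 6.1. The study is a pilot whose sample size and feasibility rule rest on two proportions, and no stated decision uses the widening. All of that stands and limits the weight of the point. The statement is nevertheless placed under the plan's hypothesis, and the tests listed beside it do not address it.

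Second, the planned output is not silent. Under the widening scenario the pre-implant mean gap exceeds the pre-mastectomy one in 98% to 100% of trials, so direction can be read. If the correlation is assumed non-negative, setting it to zero gives a conservative interval: with SD 0.8 °C the half-width is 0.56 °C, against 0.40 °C at ρ = 0.5. That stands too, but it leaves the reader to assemble a rough interval that the investigators could report exactly.

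Third, 18 is the expected number consenting. If 90% of them have complete readings, about 16 remain, and section 5.1 does not allow a missed pre-implant reading to be replaced after implant placement. With 16 patients, power for 0.5 °C falls to 0.88 / 0.65 / 0.47. With 11, the fewest complete patients that section 6.2 still accepts, it is 0.70 / 0.47 / 0.32. This is fair, and it favours an interval over a significance test.

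Finally, three contrasts, each also split into flap and core, make nine intervals in a small sample, and single-step tests have power of only 0.17 to 0.39. One overall contrast, or labelling the widening as descriptive, would remove the mismatch. A label alone, however, would leave the uncertainty unreported.

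**Conclusion.** The concern holds. Section 6.3 hypothesises a widening gap and plans nothing that estimates or tests it, and no other section supplies the analysis. What is missing is a measure of uncertainty for the within-patient change. Its direction will be visible from the three means.

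With 18 patients and an assumed SD of change of 0.6 to 1.0 °C, the direct contrast would have a 95% CI half-width of about 0.30 to 0.50 °C and power of 0.92 to 0.52 for an overall widening of 0.5 °C. Without it, an apparent widening of at least 0.2 °C would arise by chance in 8% to 20% of trials with a constant gap. These sizes depend on SDs that the documents do not give. The mismatch itself does not. It should be corrected before analysis, but it does not touch the feasibility conclusions or the flap-versus-core comparisons.

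**What to change.** Keep the three t-tests and add to section 6.3:

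> For each patient and time point, the gap is core temperature minus mean flap temperature, averaged over quadrants and breasts. We will estimate the mean within-patient change in gap from pre- to post-mastectomy, from post-mastectomy to pre-implant, and overall from pre-mastectomy to pre-implant. Each will be given with a 95% confidence interval from paired differences, in patients with readings at both time points, and that number will be stated. Changes in flap and in core temperature will also be reported separately, because core temperature is actively managed during surgery. These contrasts are supportive estimates, without multiplicity adjustment.

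The overall change is the main answer to the widening question. The two step contrasts are useful as estimates, not as tests. The plan should also say which core reading is used if the two breasts of a bilateral patient reach a time point at different times, since the documents do not specify this.

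The cost is a few sentences, slightly more analysis work and a few more reported intervals. No new data or patients are needed.

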## **Mastectomy Flap Temperature and Clinical Implications**

Wake Forest Baptist Comprehensive Cancer Center

WFBCCC # 74222

Additionally, we will explore the relation between average mastectomy flap temperature and number and degree of post-surgical complications for up to 90 days post-surgery, to examine whether patients with cooler mastectomy flaps intraoperatively have increased surgical complications compared to patients with warmer flaps. While there is a possibility that the presence or absence of cancer can affect surgical complication rates, we do plan to include patients undergoing both therapeutic and prophylactic mastectomy in this study. When performing data analysis, complications are recorded by breast rather than by patient allowing us to note which breasts undergo mastectomy for therapeutic reasons and which are prophylactic.

If we are successful in showing feasibility in our primary objectives, we hope that these pilot data will ultimately aid in future, large interventions designed to warm or precondition mastectomy flaps in efforts to optimize surgical outcomes for implant based breast reconstruction surgeries.

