### **2.3 Exploratory Objective(s)**

- 2.3.1 Quantify relationship between flap temperatures and incidence of mastectomy surgical complications within 90 days of surgery.

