## **3.0 Patient Selection**

### **3.1 Inclusion Criteria**

- 3.1.1 Scheduled for unilateral or bilateral mastectomy with implant based breast reconstruction within the Wake Forest Baptist Health System.
- 3.1.2 Aged 18 or older.

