## **4.0 Study Outcomes and Study Measures**

### **4.1 Primary Outcomes**

5.1.1 The proportion of eligible women who consent to having mastectomy flap temperatures measured during surgery will be computed by dividing the total number of eligible women screened by the number of these women who consent. We will compute a 95% confidence interval around this proportion.

5.1.2 We will compute the proportion who successfully have all relevant flap temperatures measured (this will either be 12 or 24 total expected flap temperatures: 4 quadrants, at three time points- pre and post-mastectomy and pre-implant placement; one or both breasts), and we will compute a 95% confidence interval around this proportion.

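### The exploratory analysis in section 6.3 counts complications per patient with no stated allowance for one or two operated breasts; a breast-level description would be a cheap, minor improvement

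*Combined protocol and SAP*

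**What the plan says.** All references are to the combined protocol and SAP.

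- **Objective 2.3.1** is to "Quantify relationship between flap temperatures and incidence of mastectomy surgical complications within 90 days of surgery". It does not state whether the unit is the patient or the breast.
- **Section 6.3** will "examine whether there is a relation between the number of such complications per patient" and two exposures, both defined per patient: the gap between average flap and core temperature, and the average flap temperature itself. It names no model, offset or stratification for this relation.
- **Section 3.1** admits women "Scheduled for unilateral or bilateral mastectomy with implant based breast reconstruction", so a patient has one or two breasts at risk. Section 4.1 accordingly says there will "either be 12 or 24 total expected flap temperatures".
- **The end of section 1.0** poses the question by patient: "whether patients with cooler mastectomy flaps intraoperatively have increased surgical complications compared to patients with warmer flaps". It also says that, at the analysis stage, "complications are recorded by breast rather than by patient allowing us to note which breasts undergo mastectomy for therapeutic reasons and which are prophylactic". The reason given is a possibility, stated as no more than that, that "the presence or absence of cancer can affect surgical complication rates".
- **Elsewhere in 6.3**, the by-breast wording covers the number of readings to be obtained and the variability of temperature readings. The plan expects variability by quadrant and by breast to be weak.
- **Section 6.1** promises only that complications will be described as frequencies.

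**The concern.** The outcome is a count whose opportunity differs between patients. A woman with two operated breasts can have more complications simply because two breasts were operated on, and nothing in 6.3 says this will be taken into account.

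The exposure raises a second issue. A flap belongs to one breast. When the temperatures of two breasts are averaged, a complication in the left breast is related partly to the temperature of the right. The within-patient contrast is lost, and so is the distinction between therapeutic and prophylactic breasts that section 1.0 says can be noted.

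At stake is how easily the exploratory result can be interpreted, and its use as background for the larger intervention studies that section 1.0 hopes to inform. The two feasibility proportions and the paired flap-core comparisons do not depend on it.

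**Working it through.** **The plan's own figures.** Section 6.3 attaches no number to this analysis. The one planning figure needed is the expected number of consenting patients in 6.2: 0.60 × 30 = 18. Each breast contributes 4 quadrants × 3 time points = 12 readings, so each breast has its own average and no new measurement is needed.

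**Assumed inputs.** The documents give no per-breast complication rate and no bilateral fraction. I take:
- *p*, the risk in the first or only breast: 6%, 15% or 28%. The ends match the infection range in section 1.0; 15% is an intermediate value. Section 4.3 counts several complication types, so these are illustrative only.
- *k*, the relative risk of the second breast: 1 or 0.5.
- *f*, the bilateral fraction: 0.5, giving 9 unilateral and 9 bilateral patients, or 27 breasts.
- At most one event per breast, and independent breasts unless stated.

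**Step 1: expected count.** Unilateral *p*; bilateral *p*(1 + *k*); ratio 1 + *k*.
- *k* = 1: ratio 2.0 (0.06 against 0.12; 0.28 against 0.56).
- *k* = 0.5: ratio 1.5.
- Bilateral share of expected events, *f*(1 + *k*) / [*f*(1 + *k*) + 1 − *f*]: 1.0/1.5 = 67%, or 0.75/1.25 = 60%.

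**Step 2: how much noise.** Share of the variance of the count due to laterality = *f*(1 − *f*)(*kp*)² / [*f*(1 − *f*)(*kp*)² + *p*(1 − *p*) + *f·kp*(1 − *kp*)].
- Example, *p* = 0.28, *k* = 1: 0.0196 / (0.0196 + 0.2016 + 0.1008) = 6.1%.

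| | *p* = 6% | 15% | 28% |
|---|---|---|---|
| *k* = 1 | 1.1% | 2.9% | 6.1% |
| *k* = 0.5 | 0.3% | 0.9% | 1.8% |
| *k* = 1, within-patient correlation 0.3 | 0.9% | 2.4% | 5.1% |

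These shares are small. A broader endpoint with more events would raise them.

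**Step 3: when noise becomes bias.** I used a simulation with 18 patients, half bilateral, Poisson counts per breast, temperature correlation 0.5 between breasts, no true temperature effect, a Spearman test at 5% and 2,000 replicates. The columns are per-breast mean counts.

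| Rejection rate | 0.15 | 0.35 | 0.60 |
|---|---|---|---|
| No temperature difference by laterality, raw count | 5.1% | 5.5% | 5.7% |
| Bilateral patients 1 SD cooler (assumed), raw count | 5.9% | 6.8% | 8.2% |
| Same, count divided by number of breasts | 5.9% | 6.0% | 5.5% |

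Simulation error is about 0.5 points per entry (square root of 0.06 × 0.94 / 2,000). Without a laterality-temperature link there is no visible bias. Even with an assumed 1 SD shift, the effect at this sample size is small.

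**Step 4: what a breast-level description could show.**
- Expected affected breasts, 18*p* + 9*kp*: 1.6 to 7.6 (*k* = 1) or 1.4 to 6.3 (*k* = 0.5).
- Expected discordant bilateral pairs at *k* = 1, 9 × 2*p*(1 − *p*): 1.0 to 3.6; multiplied by 0.7 for within-patient correlation 0.3, 0.7 to 2.5.
- Chance of no event at *p* = 6%: 0.94^27 = 19% (*k* = 1); 0.94^18 × 0.97^9 = 25% (*k* = 0.5).

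The breast-level contrast would therefore be thin if rates are in this range.

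**The case against.** The patient level is a legitimate choice. Section 1.0 itself asks about patients with cooler flaps, patients are the independent units, and core temperature is one value per patient at each time point. The analysis is exploratory, and 6.3 names no model, so adjustment for laterality is unstated but not excluded. The plan also expects temperature to vary little between breasts; if so, separating them recovers little. All of this stands, and it is why the point is minor.

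The magnitude figures can also be faulted. They borrow an infection range, treat each breast as having at most one event, and assume the bilateral fraction. That is fair: they show scale and do not predict the planned count.

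Three stronger readings are tempting, and the documents do not support them.
- *That the relation is confounded or its error rate inflated.* This requires flap temperature to differ by laterality, and no section says that it does.
- *That 6.3 contradicts section 1.0.* Recording by breast is compatible with summing per patient, and the frequencies in 6.1 are only a shorter summary.
- *That breast-level data will not exist because Table 1 names no laterality or affected-breast field.* Section 5.1 says the data "will include (but not be limited to) that shown below in Table 1", and section 1.0 says complications are recorded by breast.

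What remains is that the stated analysis has an uneven denominator and makes no use of by-breast information that the plan says it will hold.

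**Conclusion.** The point holds as a minor improvement to an exploratory objective. Section 6.3 states no allowance for one or two breasts at risk. The expected count for a bilateral patient is 2.0 times that of a unilateral patient at equal per-breast risk, or 1.5 times if the second breast has half the risk; both are assumptions. The likely consequence is modest noise. The loss of the link between a complication and its own flap's temperature does not depend on any assumed rate, but its practical value depends on how much the two breasts differ, which the plan expects to be little. The primary feasibility conclusions, the secondary flap-core comparison and the sample size are unaffected.

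**What to change.** In section 6.3, make the breast the unit of the exploratory description:

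- Relate the number and degree (major or minor) of complications in each breast to that breast's own average flap temperature and its flap-core difference. Keeping number as well as degree preserves what section 1.0 sets out to explore.
- Report it descriptively, by laterality and by therapeutic or prophylactic indication.
- Give intervals that allow for clustering by patient only if event numbers permit. Otherwise tabulation is enough.

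If the per-patient count is kept, stratify by or adjust for laterality. An offset of log(number of breasts) is suitable only if equal risk per breast is accepted, because it fixes the ratio at 2.0.

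The cost is a few sentences in 6.3 and slightly more analysis, with no added patients, visits or measurements. Estimates will stay imprecise with about 18 consenting patients, and the text should say so.
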